Official Title:	Improving Health Outcomes of Migraine Patients Who Present to the Emergency Department
NCT Number:	NCT04281030
Study Number:	16-00548-2
Document Type:	Study Protocol and Statistical Analysis Plan
Date of the Document:	
• June 25, 2020

Research Protocol Addendum Aim #2

Improving Health Outcomes of Migraine Patients who Present to the Emergency Department

This addendum serves to provide additional information to main protocol (uploaded on Research Navigator). A full bibliography can be found in the main protocol.

Purpose of the Study and Background

Purpose of the Study

Aim 2: Examine the impact smartphone-based PMR on migraine quality of life, frequency, intensity, and disability.

Aim 3: Determine whether markers such as stress, anxiety and mood disorders predict patient response to an ED-initiated PMR therapy. High levels of baseline pain, scores on the Perceived Stress Scale and the PROMIS anxiety and depression measures may predict response to the comprehensive intervention on migraine disability.

Background

The ED is a critical point of contact with the health care system for many migraine patients; in current practice, it is a missed opportunity to initiate and establish a comprehensive migraine management paradigm. Behavioral headache treatments (e.g., progressive muscle relaxation (PMR), biofeedback, cognitive-behavioral therapy (CBT)) are effective migraine treatment options that are essentially free of side effects.³¹ Behavioral treatments have enduring benefits³² and may be less costly than pharmacologic interventions.³³ PMR is a standardized, evidence-based behavioral treatment used for migraine since the 1980s.^{34,35} PMR has also been successful as a technique that patients can do independently.^{36,37}

Migraineurs in the ED continue to experience pain and are discharged without adequate treatment plans. Less than 25% of ED migraine patients are pain-free on discharge.^{39,40} For most patients, headache returns within 24 hours of discharge.⁴⁰ About 40% of patients are not prescribed medication at discharge⁴⁰ and most patients are not advised to follow-up with a physician.^{40,41} There are no clear guidelines for ED management of migraine.⁴² Therefore, a simple, effective comprehensive intervention is needed for patients who present to the ED with migraine.

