Patients who have had Cognitive Behavioral Therapy, Biofeedback or other Relaxation Therapy in the past year; Cognitive deficit or other physical problem with the potential to interfere with behavioral therapy; Alcohol or other substance abuse as determined by self-report or prior documentation in the medical record; Unable or unwilling to follow a treatment program that relies on written and audio recorded materials; Not having a smartphone.

Vulnerable Subjects

N/A

Methods & Procedures

Methods & Procedures

Aim 1 has been completed. We are proceeding with the Methods & Procedures for Aim 2:

Aim 2: Examine the impact smartphone-based PMR on migraine quality of life, frequency, intensity, and disability. The primary outcome is to assess whether use of PMR in the ED improves migraine quality of life (MSQv2) at 3 months post ED-discharge (or post enrollment date if recruited post ED discharge). All subjects (N=90) will complete a migraine quality of life assessment and track their headache frequency and intensity using our APP. The smartphone app will be used to monitor adherence.

The non-traditional Research Volunteer (RV) or Research Assistant (RA) will obtain subject consent for the study.

In the light of COVID-19 and increased participant preference for remote visits, we will also recruit subjects via telephone and electronic consent will be obtained via REDCap. Following this, the initial enrollment visit will be scheduled and completed via Webex. The followup data points will continue to be collected via followup calls or emails as approved previously.

The NYU Headache Research Program has been recognized for its solid training of pre-health students in research methods. In fact, it received the first ever City College of New York S Jay Levy Fellowship for Future Leaders Distinguished Internship Host Award (2017-2018).

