All subjects will be given a \$60 gift card incentive for participating, and will receive an additional \$1 per day they do the intervention to compensate them for study-related time and data usage costs. If they complete the intervention more than 80% of the total 60 days of the study, then the daily compensation will be doubled. In addition, they will receive \$15 gift cards for the one month and two month f/u emails/calls and \$25 gift cards for the 3 month and 6 month f/u email or phone assessments. Thus, based on the prior adherence data, the max total projected amount that participants will receive is \$200 but if they get the bonus, they could get up to \$260.

This payment is on par with other migraine smartphone studies throughout the country.

Fidelity monitoring will be conducted as in Aim 1.

Data Analysis and Data Monitoring Analysis Plan

Sample Size: The sample size was calculated for the primary outcome (Δ MIDAS) and the secondary outcome (number of headaches/30 days). A study of medication plus behavioral therapy for migraine as compared with medication alone in the outpatient setting showed that the distribution of MIDAS at baseline or 3 months was right-skewed, but the Δ MIDAS was symmetric and approximately normally distributed. Considering Δ MIDAS as the primary outcome can reduce data skewedness and improve study power. Based on the study, the standard deviation (SD) of Δ MIDAS ranges from 5 to 7. With the conservative estimate of SD=7, group sample sizes of 31 and 31 achieve 80% power to detect a clinically significant difference of 5 between the groups, assuming

group standard deviations of 5 and a significance level of 0.05 using a two-sided two-sample t-test. The emergency medicine studies had over 90% follow-up at 3 months and the electronic headache diary studies' follow-up was between 76%–80%. To accommodate potential dropout rate as high as 30%, a total of 90 subjects will be recruited.

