Quality Control: The Clinical Data Monitor will download the data from the Diary Cloud Server. From this download, standard reports including missing days or entries as well as identification of any safety concerns will be created from the downloaded database and examined and reviewed by the Clinical Data Monitor.

Measurements: Our primary outcome, the Migraine Quality of Life (MSQv2) is a validated quality of life measure. In addition, we will check the Migraine Disability Assessment Scale (MIDAS), measures disability over the past 3 months. MIDAS scores were shown to have excellent test-retest reliability, high internal consistency and high external validity using a variety of measures including diary based measures. MIDAS scores are also associated with physician judgements about the severity of headache and the need for treatment. A decrease of 3 points in the MIDAS score corresponds to a one day reduction in headache related disability per month, a clinically meaningful difference. In the Headache Management Trial, persons with headache were randomized to coordinated, guideline-based care vs. usual care. The study was designed to detect a 5-point difference in MIDAS decline between treatment arms and found a highly clinically significant 7 point decline. We will examine the change in disability scores (Δ MIDAS) defined as the difference between MIDAS scores at 3 months and at baseline.

Data Storage and Confidentiality

Each subject will be assigned a unique alphanumeric identifier for use with the app. No PHI is being given to IRODY. The alphanumeric identifiers will be unrelated to the identity of the study subjects. All clinical data/information will be entered into the RedCap database. Only the PI and the RVs/RAs will have access to the linking database.

The consent forms will be kept in a separate locked file cabinet in the Tisch ED. They will be transferred periodically to a locked cabinet at [name]. If someone were to gain illegal access to the locked filing cabinet with study data, they would have no way to link this data to any identifying information.

The research team will perform all data analyses. Data will be stored electronically in a secure research database and will be available for the research team.

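### The addendum names no baseline-adjusted model for the Aim 2 comparison; adjusting ΔMIDAS for baseline MIDAS is a cheap gain in precision

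*Combined protocol and SAP*

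**What the plan says.** The document describes its own scope: "This addendum serves to provide additional information to main protocol". The main protocol is not supplied, so what follows concerns the addendum only.

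- **Measurements:** ΔMIDAS is "defined as the difference between MIDAS scores at 3 months and at baseline". It is to be examined; no test or model is named.
- **Sample Size, ΔMIDAS:** "The sample size was calculated for the primary outcome", identified there as ΔMIDAS. The calculation assumes "group standard deviations of 5 and a significance level of 0.05 using a two-sided two-sample t-test", although the same sentence opens with an SD of 7. ΔMIDAS was preferred partly for power and partly because "the distribution of MIDAS at baseline or 3 months was right-skewed" while the change was about symmetric.
- **Sample Size, headache counts:** nonparametric tests are named for this secondary outcome only.
- **Methods & Procedures, Aim 2:** the primary question is whether PMR "improves migraine quality of life (MSQv2) at 3 months post ED-discharge". Measurements also calls MSQv2 primary. No test, model, SD or target difference is given for it.
- **Study Design, Aim 3:** the only regressions in the document. They are exploratory, cross treatment with baseline pain, psychiatric comorbidity and stress, and use variable selection. Baseline MIDAS and baseline MSQv2 are not among the named factors.
- **Collection of MSQv2:** it is added to the questionnaires at 1, 2, 3 and 6 months. A T0 assessment exists, but its instruments are not listed.

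**The concern.** Subtracting baseline is a form of baseline adjustment, but with the slope fixed at 1. When the true slope of the 3-month score on baseline is below 1, the change score over-corrects and carries avoidable variance. Regression on baseline estimates the slope and removes that variance. Because ΔMIDAS already requires baseline MIDAS, the covariate costs no extra data collection.

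Three things are at stake. The first is precision in a pilot that may finish with 31 evaluable subjects per arm. The second is sensitivity to chance baseline imbalance between small arms. The third is that, with no model stated, the choice between adjusted and unadjusted results remains open. Bias is not at stake: under randomisation both estimators target the same effect.

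**Working it through.** **Inputs from the Sample Size paragraph.** Difference 5; SD of ΔMIDAS 5 to 7, with 7 taken as conservative; 31 per group; two-sided 0.05; 30% dropout; total 90; cited follow-up of 76% to 80% and over 90%.

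**Inputs assumed, because the documents do not give them.** ρ, the correlation of baseline and 3-month MIDAS, from 0.3 to 0.9; k, the 3-month SD divided by the baseline SD, at 0.8, 1 and 1.2; equal allocation.

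**Step 1: the plan's own figure.**
- Normal approximation: n = 2(1.96 + 0.842)² × 7²/5² = 30.8, so 31 per group.
- Exact t: noncentrality 5/(7√(2/31)) = 2.81 on 60 df gives 79.0% power; 32 per group would be needed for 80%.
- Dropout: 62/0.7 = 88.6, so 89; by arm, 31/0.7 = 44.3, so 45 and a total of 90.

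The stated 31 and 90 are therefore reproduced with SD 7. The SD of 5 in the same sentence does not give 31; it needs 16 per group (17 by exact t).

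**Step 2: variance after adjustment.** With baseline SD s, Var(Δ) = s²(1 + k² − 2ρk), held at 49. The residual variance given baseline is s²k²(1 − ρ²). The ratio is

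k²(1 − ρ²)/(1 + k² − 2ρk), which is (1 + ρ)/2 when k = 1.

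There is no gain when ρk = 1, because the change score then already uses the right slope. For k = 1.2 that is ρ = 0.83.

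**Step 3: power at 31 per arm, difference 5, SD(Δ) 7.** Simulated with the slope estimated and 59 df, 100,000 runs per cell. Unadjusted power was 78.9% to 79.2% throughout.

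| ρ | k = 1 | k = 1.2 | k = 0.8 |
|---|---|---|---|
| 0.3 | 92.5% | 88.3% | 97.2% |
| 0.5 | 88.6% | 83.9% | 95.3% |
| 0.7 | 84.5% | 79.7% | 93.2% |
| 0.8 | 82.3% | 78.5% | 92.8% |
| 0.9 | 80.3% | 79.2% | 94.0% |

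For k = 1.2 the change against the unadjusted test is +9.3, +4.6, +0.8, −0.6 and +0.2 points, reading down.

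**Step 4: better follow-up (k = 1, SD 7).** 45 × 0.76 = 34.2, 45 × 0.80 = 36 and 45 × 0.90 = 40.5, so about 34, 36 and 40 per arm. Unadjusted power is 83%, 85% and 88%. Adjusted power, for ρ from 0.9 to 0.3, is 84–95%, 86–96% and 90–97%.

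**Step 5: smaller SD (31 per arm).** At SD 6, unadjusted power is 89.8%, against 90.7%, 92.1% and 93.5% adjusted at ρ 0.9, 0.8 and 0.7 (k = 1). At SD 5, unadjusted power is already 97%.

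**Step 6: skewed baseline.** With baseline skewness of 1 to 2.3 and symmetric change (k = 1, SD 7, 31 per arm), adjusted power is 81–92% against 79–80% unadjusted. Adjusted type I error is 4.3–5.0%.

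**Step 7: chance imbalance.** At ρ = 0.5 and k = 1 the implied baseline SD is 7/√(2 × 0.5) = 7. One standard error of baseline imbalance is 7√(2/31) = 1.78 points. It shifts the unadjusted change difference by (1 − 0.5) × 1.78 = 0.89 points, against a target of 5.

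**MSQv2.** No calculation is possible without an SD or a target difference.

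**The case against.** The case for leaving the plan alone has real content.

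- **Validity.** A change-score comparison is valid under randomisation, and the plan gives a distributional reason for it. This stands: the point is efficiency, not error.
- **Size.** Neither ρ nor k is in the documents. At high ρ the gain is one to three points with equal variances, and about nil if the 3-month SD is larger than at baseline. The large gains need low ρ or k below 1. Measurements credits MIDAS with excellent test-retest reliability; that does not fix the 3-month correlation, but it lends no support to low values. This stands as a limit on size.
- **Corner case.** The main figures use the largest SD and the worst follow-up. The plan also says "The emergency medicine studies had over 90% follow-up at 3 months", and at 90% follow-up unadjusted power is already 88% at SD 7. This also stands.
- **Target.** Every figure concerns ΔMIDAS, whereas two sections call MSQv2 primary and never confirm it at T0. This is why the primary outcome must be settled first and why the MSQv2 advice is conditional.
- **Unseen main protocol.** It may hold a fuller plan. The point is confined to the addendum.
- **Timing.** The document does not say whether Aim 2 outcomes had already been collected or viewed in June 2020, so it cannot be claimed that a model added now would precede the data.

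The Aim 3 regressions are not an answer. They are exploratory searches for predictors of response and do not name the baseline outcome score.

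None of this gives a reason to prefer the unadjusted test: across the scenarios run, the worst loss is about 0.6 points and the gain reaches 13 points or more.

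**Conclusion.** The concern holds. Within this addendum, no baseline-adjusted Aim 2 analysis is stated, ΔMIDAS is tied only to a sizing t-test, and MSQv2 has no method. On the plan's conservative inputs (31 per arm, difference 5, SD 7), adjustment moves power from 79% to between 80% and 93% with equal variances. Under k = 1.2 the result lies between a 0.6-point loss and a 9.3-point gain; under k = 0.8 power is 93% to 97%. These sizes rest on assumed ρ and k and apply to ΔMIDAS only. At SD 5, or with good follow-up and high ρ, little changes. This is a change the plan should make for precision and pre-specification; the randomised comparison is not invalid without it. Confidence is medium, mainly because the main protocol is unseen and the correlation is unknown.

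**What to change.** 1. Reconcile the primary outcome: MSQv2 in Methods & Procedures and Measurements, ΔMIDAS in Sample Size.
2. State that 3-month ΔMIDAS is analysed by linear regression on arm plus baseline MIDAS, with the unadjusted t-test as a sensitivity analysis. Regressing the 3-month score instead of the change gives the same treatment estimate.
3. Specify residual and leverage checks, because baseline MIDAS is described as right-skewed.
4. Confirm whether MSQv2 is collected at T0. If so, analyse 3-month MSQv2 by linear regression on arm plus baseline MSQv2.
5. If the main protocol already contains these models, cross-refer to it instead.

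The cost is a few sentences of analysis-plan text, one degree of freedom and slightly more analysis work. N stays at 90. If the 3-month SD exceeds the baseline SD by about 20% and ρ is near 0.8, about 0.6 points of power are lost.
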